The following information impacts the A5360 study and must be forwarded to your institutional review board (IRB)/ethics committee (EC) as soon as possible for their information and review. This Letter of Amendment (LOA) must be approved by your IRB/EC before implementation.

The following information may also impact the Sample Informed Consent. Your IRB/EC is responsible for determining the process of informing participants of the contents of this LOA.

Upon receiving final IRB/EC and any other applicable regulatory entity approvals for this LOA, sites should implement the LOA immediately. Sites are still

required to submit an LOA registration packet to the DAIDS Protocol Registration Office (PRO) at the Regulatory Support Center. Sites will receive a registration notification for the LOA once the DAIDS PRO verifies that all required LOA registration documents have been received and are complete. An LOA registration notification from the DAIDS PRO is not required prior to implementing the LOA. A copy of the LOA registration notification, along with this letter and any IRB/EC correspondence, should be retained in the site's regulatory files.

The main reasons for this LOA are to clarify the requirement that the participant must contact the site to report taking the last pill of study drug (SOF/VEL), including adding this information to the sample informed consent; to add information on laboratory requirements for CD4+ post-entry; and to update the protocol team roster. These changes were identified by the team.

The following are changes to A5360 FINAL Version 1.0, dated 01/10/18:

1. Per a new regulatory requirement by the Division of AIDS (DAIDS), a Protocol Signature Page (PSP) is appended for submission to DAIDS Protocol Registration System (DPRS) as part of the LOA registration packet.
2. Section 5.1.2, Administration and Duration: The first paragraph has been revised to read:

Participants will take SOF/VEL orally once daily with or without food and will receive treatment for a duration of 12 weeks. Study staff will observe the first dose being taken by the participant upon completion of all entry evaluations.

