At entry (Step 1), all participants will receive the entire study-provided treatment supply, following study entry procedures, with the first dose being observed by study staff. The next planned study visit is the key primary outcome evaluation for SVR, scheduled at week 24. There will be no planned interim in-person study visits with participants between entry and week 24. Detailed locator information will be collected at entry (see section 6.3.21). In lieu of resource intensive in-person study visits, between entry and

the primary outcome evaluation at the week 24 visit, sites will contact participants at weeks 4 and 22, via a remote mechanism based upon the participant's choice and availability, in order to assess adherence status at week 4 and to schedule the SVR evaluation visit at week 24, as well as update the locator information. At week 4, the participant will be asked if he/she is taking the study medication and about adherence, changes in contact information, and reminders for the study visit for SVR evaluation. If participants report sub-optimal adherence or that they are not taking their HCV medication, they will be read (if a phone contact) or message (if remote contact is via email/text message/WhatsApp) a standard script highlighting the benefits of HCV therapy and the importance of adherence. They will also be asked about reasons for their non-adherence and then receive standardized encouragement and clarification about the medication and importance of adherence. There will be no further site-initiated interaction with the participant until week 22, at which time participants will be queried about any changes to their contact information and will also be reminded of their upcoming SVR visit. These contacts are designed to help keep participants engaged with the study and keep their contact information up to date in order to minimize LTFU prior to the primary outcome- evaluation of SVR. Resource utilization, including staff time (both for remote contact as well as unplanned study visits) and any associated laboratory or other tests ordered during unplanned clinic visits (e.g., Magnetic Resonance Imaging [MRI], ultrasonogram, blood tests) will be documented, translated to costs using reimbursement rates from WHO CHOICE and the U.S. Center For Medicare and Medicaid Services, and incorporated into the cost analysis.

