5.1.2 Administration and Duration

Participants will take SOF/VEL orally once daily with or without food and will receive treatment for a duration of 12 weeks. Study staff will observe the first dose being taken by the participant upon completion of all entry evaluations. Participants should be instructed to open and finish one bottle of study product at a time. When the participant takes the last pill of SOF/VEL from each bottle, he/she will be instructed to contact the site to report the completion of the bottle. Participants will, therefore, contact a site a maximum of three times to indicate completion of a bottle. See A5360 MOPS for additional information on reporting of treatment stop date.

In the scenario of lost study medication, the participant will be asked to contact the study site as soon as possible. If the participant has been off study medication less than 2 weeks (≤ 14 days), he/she will be eligible for a one-time replacement of study medication to complete the 12 week course. Participants who report a subsequent loss of study medication will not be eligible for replacement and will enter the follow-up phase (week 24 visit). If the participant has not taken study medication for more than 2 weeks (≥ 15 days), study medication will not be replaced and the participant will enter the follow-up phase (week 24 visit).

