6.3.15 Questionnaires

Adherence Assessment

Adherence will be captured at the week 4 remote contact (see section 6.3.22) and week 24/SVR evaluation visit (i.e., week 22 or beyond). At both assessments, participants will be asked to estimate their adherence using Likert-type questions (all, most, half, some, or none). At the SVR visit, participants will also be asked to indicate the percentage of study medication that they actually took on a visual analog scale. At the week 4 remote contact assessment and week 24/SVR evaluation visit, participants who report less than perfect adherence will be asked about barriers to adherence.

Health Outcomes Questionnaire (EQ-5D)

The EQ-5D is a validated instrument used to collect data about quality of life (<http://www.euroqol.org>). The instrument asks questions and each has three possible responses (EQ5D-3L version). The instrument asks respondents to comment on their degree of mobility, self-care, usual activities, pain/discomfort, and anxiety/depression, and then ask participants to record their current health-related quality of life state using a vertical visual analogue scale (0-100 range). The instrument has been translated into a variety of languages and is available as a paper form, a computer-based form, a tablet/cell phone form, or as an interview.

Responses must be recorded on an eCRF from the entry visit and week 24/SVR evaluation, and weeks 48 and 72 visits. In addition, responses must be recorded in the event of an unplanned study visit.

Health Care Utilization Questionnaire

The health care utilization questionnaire solicits participant-reported health care utilization in the past 4 weeks including: 1) nights spent in a hospital bed, 2) visits to an emergency department, and 3) visits to a doctor's office. This questionnaire will be administered during visits at entry, week 24/SVR evaluation, and weeks 48, 72, and any unplanned visits. Responses must be recorded on an eCRF.

Substance Use Questionnaire

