6.3.22 Remote Contact with Participants Outside of Planned Clinic Visits

When contacting participants remotely, sites will have the flexibility to make adjustments to the mode of contact utilized at their discretion and at the participant's convenience – the only mode that will not be allowed is to schedule clinic visits in place of the remote contact. Sites will also be able to use different modes to contact different participants. Additionally, how the participant was contacted (i.e., mode of contact) will be collected on the eCRF.

Data that will be captured from the participant during the week 4 remote contact is whether the participant is taking study medication (i.e., adherence), in the prior 4 weeks. All participants will receive an individually tailored message, based on their adherence, which will be read or written to them in order to promote and/or encourage adherence through the end of treatment. The message will highlight the benefit of treatment for HCV and the importance of adherence and will be tailored to each participant's response as to how well he/she is adhering to the HCV treatment regimen. Additionally, at both weeks 4 and 22, locator information will be updated (if anything has changed) and participants will be reminded to return for their SVR evaluation visit. Sites will be allowed to contact and collect participant's responses on adherence and to update his/her locator information using any of the options listed above, namely phone call, text message, email, or social media (e.g., WhatsApp, Facebook Messenger, Twitter, etc.; for a complete list, please refer to the MOPS). If the participant comes in for the week 24 visit prior to the completion of the week 22 remote call, or if the participant has completed the discontinuation visit, then the week 22 remote call is not needed.

The remote contact is not designed to assess concomitant medications or AEs. At the end of each remote contact, participants will be reminded that the information that they shared will not be communicated to the study team and that if they have concerns about symptoms or study questions they should contact the site via the telephone number provided by the site. This information should be reported in a medical record then reviewed and entered into an eCRF at the week 24/SVR evaluation visit.

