10.6.3 Secondary Outcomes Analysis

Premature discontinuation of study treatment will be defined from participant self-report either via remote contact prior to SVR evaluation, or at an unplanned visit or by retrospective recall at the week 24 or SVR evaluation visit (whichever occurs first). Those participants missing information from all these mechanisms will be assumed to have prematurely discontinued. The proportion of premature study treatment discontinuation will be estimated and a CI calculated to summarize the range of plausible values using methods parallel to other dichotomous outcomes described above.

Non-serious AEs will be summarized by the Medical Dictionary of Regulatory Affairs (MeDDRA) System Organ Class by the reporting types described in section 7.2.

Those who do not achieve SVR with an observed HCV RNA \geq LLOQ will have both baseline and SVR specimens tested for HCV RASs. Participants in this subset with HCV RASs present in their SVR specimen that were not present in their baseline specimen will be enumerated along with the relative frequencies of new RASs. A description of the observed RASs will also be provided.

Among SVR responders, HCV RNA post SVR follow-up (i.e., Step 2) will be used to evaluate for the HCV reinfection outcome. Detectable HCV RNA, with and HCV sequence distinct from the baseline sequence will qualify for the outcome of HCV reinfection. The absolute number (and relative frequency) of participants meeting this outcome will be summarized along with a 95% CI using methods as described for other dichotomous study outcomes.

Among SVR responders, HCV disease regression will be defined by the absolute change between baseline FIB-4 value and the final study FIB-4 value. The distribution of these absolute changes will also be described using key percentiles.

Further details are outlined in the study's Statistical Analysis Plan (SAP).

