4.2.3 Secondary Outcome Measure #3 – Premature Discontinuation of HCV medications

Measure Title: Percentage of Participants who Prematurely Discontinued HCV Study Medications

Measure Description: Premature discontinuation was defined by participant self-report, as there were no planned clinic visits during the 12 week study medication period. Participants discontinuing study follow-up without information about completion of HCV study medications were counted as having prematurely discontinued medications.

A two-sided, 95% confidence interval was calculated for the percentage using the Wilson (score) method.

Time Frame: From treatment initiation to SVR12 evaluation.

Population Description: Participants who enrolled into study and received first dose of study medication.

Associated study objective: “To estimate the proportion of participants who prematurely discontinue HCV treatment.”

Details: Since participant reporting of the timing of stopping study treatment may be by participant recall more than 12 weeks after the fact, premature discontinuation will be defined by the final treatment dose date being fewer than 11 weeks (or fewer than 77 days) post initial dose accounting for reported treatment interruptions. The timing and reasons for premature discontinuation will be summarized, as those details are available in the study database. As available, any other details on the disposition of study treatment (e.g. treatment interruptions), will be summarized.

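### The week 22 contact does not ask whether treatment was finished, so completers who report nothing and never return are counted as early stoppers

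*Protocol*

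**What the plan says.** Protocol Section 10.6.3 lists these sources for premature discontinuation: "self-report either via remote contact prior to SVR evaluation, or at an unplanned visit or by retrospective recall at the week 24 or SVR". The last source is the clinic visit at which SVR is assessed. The section then gives the rule for missing data: "Those participants missing information from all these mechanisms will be assumed to have prematurely discontinued". SAP Section 4.2.3 words that rule differently: "Participants discontinuing study follow-up without information about completion of HCV study medications were counted as having prematurely discontinued medications". The SAP also sets the cut-off at fewer than 77 days after the first dose, because recall may reach back more than 12 weeks.

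Two remote contacts are scheduled before the SVR visit. The week 4 contact asks about adherence. For week 22, Protocol Section 3.0 describes a contact "at which time participants will be queried about any changes to their contact information and will also be reminded of their upcoming SVR visit". Section 6.3.22 gives it the same content. Section 6.3.15 and Table 6.1-1 place adherence assessment at week 4 and at the week 24/SVR visit only.

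There is also a report that the participant makes. Base Section 5.1.2 reads: "When the participant takes the last pill of SOF/VEL from each bottle, he/she will be instructed to contact the site to report the completion". The letter of amendment that revises Sections 5.1.2 and 6.3.10 limits this to the third bottle, and gives as one of its reasons clarifying that "the participant must contact the site to report taking the last pill of study drug (SOF/VEL"). Section 6.3.10 sends that self-report to the eCRF even when it is made outside a visit.

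**The concern.** Section 10.6.3 counts remote contact as a source of information on discontinuation, yet neither scheduled contact is set up to show completion. Week 4 comes too early, and week 22 does not ask. After week 4, the site learns whether the course was finished only if the participant takes the initiative or comes to the clinic.

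What is at stake is the meaning of this secondary outcome. Section 2.2 names treatment completion as a risk of dispensing the whole supply at entry. It also treats taking the treatment and returning for SVR confirmation as separate components. An imputation that turns non-attendance into early stopping merges the two, and it can only push the discontinuation figure up. For late attenders, the answer also rests on long recall.

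**Working it through.** **1. When completion can be learned.** Scheduled end of treatment is week 12.

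| Source | Study week | Weeks from week 12 | What it can show |
|---|---|---|---|
| Week 4 contact | 4 | 4 − 12 = −8 | Adherence so far |
| Last-pill report by participant | about 12 | about 0 | Completion date |
| Unplanned visit | up to 22 | up to +10 | Treatment disposition, if volunteered |
| Week 22 contact | 22 | 22 − 12 = +10 | Locator update and reminder only |
| Week 24 visit (window weeks 22 to 28) | 22 to 28 | +10 to +16 | Adherence and treatment changes, by recall |
| Late SVR visit | up to 72 | up to 72 − 12 = +60 | The same, by longer recall |

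The week 22 contact is the only one of these that the site initiates after treatment without needing a clinic visit, and it is the one with no treatment question.

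**2. Who is affected.** For a completer to be counted as an early stopper under SAP 4.2.3, all of the following must hold: no last-pill report, no informative unplanned visit, and no SVR visit by the end of follow-up. Being reached at week 22 makes no difference.

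Protocol 10.6.3 is less clear. It imputes only when every listed mechanism is empty, and remote contact is one of them. Read literally, a week 4 answer fills that mechanism and blocks the imputation, although it cannot show completion. The SAP, which asks for information about completion, would impute the same person. Section 10.6.3 also does not name the last-pill report, so that report counts there only if it is taken to be a form of remote contact.

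**3. Size.** The documents give no expected rate or precision for this outcome, so there is no stated figure to reproduce. As a check on the method, the Wilson limits at n=400 agree with Protocol Table 10.4-3: 98% gives 96.1 to 99.0, and 90% gives 86.7 to 92.6.

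Let d be the true early stoppers, m the completers who never return and have no informative unplanned visit, and s the share of m whose completion becomes known, by last-pill report or by a week 22 question. Then

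reported proportion = [d + m(1 − s)] / 400.

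One silent completer adds 1/400 = 0.25 percentage points. The values of d, m and s are assumptions, and all 400 are assumed to start treatment.

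| d (true %) | m | s = 0: count, % (Wilson 95%) | s = 0.5: count, % (Wilson 95%) |
|---|---|---|---|
| 4 (1.0) | 4 | 8, 2.0 (1.0 to 3.9) | 6, 1.5 (0.7 to 3.2) |
| 4 (1.0) | 20 | 24, 6.0 (4.1 to 8.8) | 14, 3.5 (2.1 to 5.8) |
| 8 (2.0) | 4 | 12, 3.0 (1.7 to 5.2) | 10, 2.5 (1.4 to 4.5) |
| 8 (2.0) | 20 | 28, 7.0 (4.9 to 9.9) | 18, 4.5 (2.9 to 7.0) |

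With s = 1 the figure returns to the true 1.0% or 2.0%. The upper value m = 20 is borrowed from the review trigger in Protocol 10.5.1 (more than 20 persons not evaluable for SVR). It is a convenient scale and not a forecast.

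**The case against.** The strongest reply is that the plan already has a route for this information. Every participant is instructed to report the last pill, the report goes on the eCRF without a visit, and the SAP imputes only when nothing is known about completion. Missing week 24 is also not enough, because the SVR visit may take place up to week 72, and Section 2.2 adds an incentive to attend. This stands, and it narrows the point to silent completers who never attend. It does not close the gap. The report depends on the participant acting, and those who do not report may well be those who do not return.

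Second, the plan lists reasons for non-SVR, with early discontinuation separate from missing evaluation, and the SAP will summarise the timing and reasons for discontinuation as available. That helps a reader, but neither document commits to splitting imputed from reported discontinuations. The rule is openly stated, and it is conservative in the same way as counting missing SVR as failure.

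Third, the contact script is in the MOPS and the coding details are in the AIP, neither of which is available here. The script might contain a completion question. The protocol's own account of week 22 and its schedule do not include one.

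Fourth, remote contacts are part of the strategy under test, and Section 6.3.22 has participants told that what they share will not reach the study team. The first part carries little weight, since treatment has ended by week 22 and the question cannot change tablets taken. The second is a fair practical point, and the fix must deal with it.

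**Conclusion.** This is a cheap improvement to a secondary outcome; the SVR estimate is not affected. The week 22 contact misses a chance to learn about completion, and under SAP 4.2.3 a completer who reports nothing and never attends is counted as an early stopper. The direction of the bias is known (upward), at 0.25 points per person. Over the assumed ranges, a true 1.0 to 2.0% would be reported as 2.0 to 7.0%, with less excess the more participants report completion or are reached at week 22 and asked. The size rests entirely on assumed counts.

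A reader might infer that everyone reached at week 22 who then fails to return is recorded as having stopped early. The documents do not support that: a last-pill report, an informative unplanned visit or a late SVR visit each prevents it, and a literal reading of Protocol 10.6.3 might not impute someone who answered at week 4. Nor is recall of up to 60 weeks typical: it applies only to the latest attenders, while a visit in the week 24 window means 10 to 16 weeks.

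**What to change.** - **Data collection.** Add two items to the week 22 contact and its eCRF (Sections 3.0 and 6.3.22, Table 6.1-1): whether all three bottles were finished, and the date of the last tablet. Ask the same in any later call made to reschedule a missed week 24 visit. Amend the closing reminder in Section 6.3.22 so that participants know these answers are recorded.
- **Analysis rule.** In Protocol 10.6.3 and SAP 4.2.3, use the same wording. Any post-treatment completion report (last-pill report, week 22 answer, unplanned visit or SVR visit) is used before imputing, and a week 4 answer alone does not show completion.
- **Reporting.** Show imputed and self-reported discontinuations as separate counts beside the combined percentage.

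The cost is about a minute in a call that is already scheduled, plus the eCRF fields. Participants who are not reached remain imputed. If the week 22 contacts are already over, the analysis and reporting changes can still be made from data in hand.

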11.0 PHARMACOLOGY PLAN

Not applicable.

12.0 COST-BENEFIT ANALYSIS PLAN

The cost-benefit analysis will employ the resource utilization data collected at planned/unplanned study visits until the SVR is assessed (week 24/SVR evaluation visit) as well as SVR data and utilization data to develop an estimate of cost/SVR attained.

12.1 Objective

12.1.1 To determine the cost/SVR attained using the MINMON protocol

12.2 Primary Outcome

12.2.1 Cost/SVR attained - both globally and stratified by country - calculated using country-specific costs and expressed in US\$ 2017.

12.3 General Approach to Costing

The cost/SVR attained will be assessed from two perspectives.

12.3.1 The perspective of the clinic/program/site treating the participant (program perspective). These costs include the cost of staff, laboratory monitoring, and medications involved in delivering HCV treatment to a participant. These costs begin at week 0 and continue through the week 24/SVR evaluation. The program cost perspective is helpful to those who administer a clinic or treatment program who want to understand how MINMON would impact their program budget.

There are two cost components from the program perspective:

1. Cost of HCV medications
2. Cost of planned and unplanned study visit evaluations between week 0 and the week 24/SVR evaluation visit

12.3.2 The healthcare sector perspective—the health sector perspective is broader than the program perspective. It includes the costs of staff, laboratory monitoring and medications between weeks 0 and 24, the cost of healthcare

utilization outside of the study site between weeks 0 and 24, and any changes in utilization that may occur in the future as the result of the participant attaining SVR.

There are four cost components from the healthcare sector perspective:

1. Cost of HCV medications
2. Cost of planned and unplanned study visit evaluations between week 0 and the week 24/SVR evaluation visit
3. Cost of healthcare utilization outside of study sites between week 0 and the week 24/SVR evaluation visit
4. Cost saving (or additional cost) that may accrue because a person attains SVR and subsequently uses fewer (or more) healthcare resources. This cost saving (cost) is defined as the DIFFERENCE in healthcare utilization per month measured at the week 48 visit compared to the week 0 visit. The healthcare utilization questionnaire measures utilization over a 4-week recall period. This is defined as healthcare utilization per month. The difference in healthcare utilization per month between the week 48 assessment and the week 0 assessment is the monthly savings (or cost) attributable to attaining SVR. It will be assumed that the monthly savings (cost) applies to every month between week 24 and week 72.

In addition, because this estimate of cost savings is uncertain, sensitivity analyses will be used to explore different estimates of saving attained including: 1) difference in utilization measured at the week 72 visit and the week 0 visit, 2) difference in utilization measured at week 72 and week 48 visits. In both of these sensitivity analyses, it will be assumed that the monthly savings (or cost) we estimate applies to every month between weeks 24 and 72.

Measures of utilization will be translated to cost (expressed in currency rather than units of resources consumed) using WHO CHOICE country-specific unit costs (http://www.who.int/choice/cost-effectiveness/inputs/health_service/en/).

It will be assumed that all resource utilization between weeks 0 and 24 is related to HCV medications. As a result, the cost estimate will tend to be biased toward a higher cost/SVR attained.

The primary analysis will be conducted in an intention to treat framework, whereby participants who are LTFU and do not return for the week 24/SVR evaluation visit are assumed to be treatment failures and not counted as "SVR" in the cost/SVR attained calculation. This approach will also tend to bias results to a higher cost/SVR attained. A sensitivity analysis will explore cost/SVR when it is assumed that the rate of SVR among those lost to follow-up at week 24 is similar to the SVR rate among those with week 24 confirmation of cure.

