A Single-arm Study to Evaluate the Feasibility and Efficacy of a Minimal Monitoring Strategy to Deliver Pan-genotypic Ribavirin-free HCV Therapy to HCV Infected Populations who are HCV Treatment Naïve with Evidence of Active HCV Infection: The MINMON Study

A Multicenter Trial of the AIDS Clinical Trials Group (ACTG)

NIAID CRMS # 30103

Clarification Memo Date: 09 April 2020

ACTG NETWORK COORDINATING CENTER
Social & Scientific Systems
[name]
[name] 20910-3714
[contact]
[contact]

CLARIFICATION MEMO

DATE: April 9, 2020
TO: ACTG CTU Principal Investigators, CRS Leaders, and CTU/CRS Coordinators
FROM: A5360 Protocol Team
SUBJECT: Clarification Memo #3 for Protocol A5360 (COVID-19)

This clarification memo (CM) does not result in a change in the protocol informed consent document. The Division of AIDS (DAIDS) has determined that these protocol changes and clarifications should be implemented immediately in response to the COVID-19 pandemic, which poses a safety risk to participants and site staff. Sites do not need institutional review board (IRB) approval prior to implementing this CM.

DAIDS does not require sites to forward this CM to their IRB; however, sites must follow their IRB's policies and procedures. If IRB review of CMs is required at a site, that site must submit this document for review.

Each site should file a copy of this CM with the protocol for reference.

The main reason for this CM is to provide guidance for study visits during the COVID-19 pandemic. The instructions in this CM supersede the instructions that were in the memo released by the A5360 Protocol Team on 03/23/20 with subject “COVID-19: Temporary Pause for Protocol A5360 (MINMON Study) and Guidance for Enrolled Participants.”

All sites should contact study participants to inform them of the temporary pause in all study visits and that they will be contacted to schedule their next visit when the pause is lifted. This contact must be documented in the participant’s study file but does NOT need to be recorded on the eCRFs and reported to the A5360 core team.

When the temporary pause on study visits is lifted, sites should contact study participants to schedule their next visit. This contact can be considered the remote contact corresponding to week 42 or week 68. This contact must be documented in the participant’s study file.

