4.2 Exclusion Criteria (Step 1)

4.2.1 Positive for the presence of hepatitis B virus (HBV) surface antigen (HBsAg).

4.2.2 For cirrhotic participants, CTP score >6 corresponding to Class B or C (Please refer to the A5360 PSWP for the website link to calculate the CTP score).

4.2.3 Breastfeeding or pregnancy.

4.2.4 Known allergy/sensitivity or any hypersensitivity to components of study drug(s) or their formulation.

4.2.5 Active drug or alcohol use or dependence and other conditions that, in the opinion of the site investigator, would interfere with adherence to study requirements.

4.2.6 Acute or serious illness requiring systemic treatment and/or hospitalization within 35 days prior to study entry.

4.2.7 In HIV positive participants, presence of active or acute AIDS-defining opportunistic infections within 35 days prior to study entry.

NOTE: AIDS-defining opportunistic infections as defined by the CDC found in the following document: <http://www.cdc.gov/mmwr/preview/mmwrhtml/00018871.htm>

4.2.8 Any history of hepatic decompensation including ascites, spontaneous bacterial peritonitis, hepatic encephalopathy, hepatorenal syndrome, and/or bleeding esophageal varices prior to study entry.

4.2.9 Use of prohibited medications within the past 14 days prior to study entry (please refer to the A5360 PSWP for the list of prohibited medications).

NOTE: ART regimens must not contain prohibited medications (please refer to the A5360 PSWP for the list of prohibited medications).

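### The week 48 minus week 0 cost saving credited to SVR has a built-in rise in hospital nights, because eligibility screens them out at week 0, and the week 72 versus week 48 check cancels any stable saving

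*Protocol*

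**What the plan says.** Protocol 12.3.2 lists four cost components for the healthcare-sector perspective. The fourth is the change in utilization that follows from cure: "This cost saving (cost) is defined as the DIFFERENCE in healthcare utilization per month measured at the week 48 visit compared to the week 0". That whole difference "between the week 48 assessment and the week 0 assessment is the monthly savings (or cost) attributable to attaining SVR", and it is assumed to hold for every month between weeks 24 and 72. Section 12.6.2 carries the same week 0 to week 48 difference into cost/SVR.

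On measurement, 12.3.2 says: "The healthcare utilization questionnaire measures utilization over a 4-week recall period". Section 6.3.15 gives the items: "1) nights spent in a hospital bed, 2) visits to an emergency department, and 3) visits to a doctor's office".

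On who may enter, exclusion 4.2.6 reads: "Acute or serious illness requiring systemic treatment and/or hospitalization within 35 days prior to study entry". Section 4.4 sets no exclusion criteria for Step 2.

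Section 12.3 calls the saving uncertain and plans two sensitivity analyses. The first takes week 72 against week 0. The second takes the "difference in utilization measured at week 72 and week 48 visits". Both results are again applied to every month from week 24 to week 72. The same section names two features that push cost/SVR upward: all use in weeks 0 to 24 is charged to HCV medication, and participants lost to follow-up count as failures. It does not mention any effect of eligibility on the week 0 baseline.

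**The concern.** A before-after difference can be read as the effect of cure only if the before value shows what use would have been without cure. For hospital nights it does not. Participants enter only if they have just come through a period free of acute or serious illness that needed hospital care, and the week 0 questionnaire asks about that same period. Hospital use can then return to its ordinary level by week 48 with no help or harm from SVR, and the plan would record the return as a cost of attaining SVR, or as a smaller saving than the true one.

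The sensitivity analyses are meant to show how far the answer depends on the estimate of savings. One inherits the same baseline. The other has no pre-cure point. A reader who saw all three results could not detect the problem, and might take a near-zero week 72 versus week 48 result as evidence that cure saves nothing.

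**Working it through.** The plan states no value for the saving, so there is no figure to reproduce. The check compares the time windows and then applies the plan's own estimator.

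**1. Windows.**
- Recall at week 0: 4 weeks = 28 days (6.3.15, 12.3.2).
- Exclusion period: 35 days before entry (4.2.6).
- 28 < 35, with 35 − 28 = 7 days to spare. The recall lies wholly inside the exclusion period.
- At weeks 48 and 72 the recall is also 28 days, but no health criterion governs who is seen (4.4).

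**2. What is screened out, by item.**
- Hospital nights: those for acute or serious illness are removed. Elective stays can remain.
- Emergency visits: partly restricted, through illness that needs systemic treatment or hospitalization. Visits for minor injury or complaints are not.
- Office visits: not restricted. Care before entry might even raise them, for example when a participant is switched off efavirenz at least 14 days before entry (4.1.9).

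**3. Period of application.** Weeks 24 to 72 are 48 weeks, and 12.3.2 equates a month with the 4-week recall: 48 / 4 = 12 periods.

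**4. Estimators for hospital nights.** Let r be the background nights per 4 weeks, f the share of those nights still seen at week 0 after the screen, and e the stable fractional reduction due to cure. The documents give none of these; all are assumptions.
- True effect over the period: −12·e·r
- Week 48 minus week 0: 12·r·[(1 − e) − f]
- Week 72 minus week 0: the same expression
- Week 72 minus week 48: 12·[(1 − e)·r − (1 − e)·r] = 0 for every e
- Error of either week 0 contrast: 12·r·[(1 − e) − f] + 12·e·r = 12·r·(1 − f). This does not depend on e.

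**5. Size with no cure effect (e = 0) and f = 0.**
- r = 0.02: 12 × 0.02 = 0.24 nights per SVR responder
- r = 0.05: 12 × 0.05 = 0.60
- r = 0.2: 12 × 0.2 = 2.4

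If a quarter of nights survive the screen (f = 0.25), the ends of the range become 0.24 × 0.75 = 0.18 and 2.4 × 0.75 = 1.8.

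**6. What the three analyses would show if cure works.** With r = 0.10 and f = 0, in nights per responder over weeks 24 to 72:

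| Reduction e | True effect | Week 48 − week 0 | Week 72 − week 0 | Week 72 − week 48 |
|---|---|---|---|---|
| 0 | 0.00 | +1.20 | +1.20 | 0 |
| 0.25 | −0.30 | +0.90 | +0.90 | 0 |
| 0.50 | −0.60 | +0.60 | +0.60 | 0 |
| 0.90 | −1.08 | +0.12 | +0.12 | 0 |

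A true 50% reduction would be reported as an increase of the same size. A hospital-night saving appears only when e exceeds 1 − f: never at f = 0, and only above a 75% reduction at f = 0.25.

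**The case against.** The strongest reply is that the plan is open about the weakness. Section 12.3 calls the saving uncertain and offers sensitivity analyses, 12.6 concedes that there is no control arm, and the hospital-night error runs in the same direction (higher cost/SVR) as the biases already accepted. The objective is exploratory, and the Primary SAP (2.1 and 3.3) leaves such objectives to separate plans. All of this is true and limits the weight of the point. It does not answer it: the uncertainty is acknowledged, but its source is not named, and neither sensitivity analysis can expose it.

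It is also fair that the healthcare-sector perspective is defined to include later changes in use. Removing component 4 from the base case would change that perspective and in effect assume no saving. The point does not need that step.

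Four stronger readings are tempting, and the documents do not support them.
- *The entry criteria fix the sign of the whole term.* They do not, because office visits are unrestricted and may be raised before entry.
- *Most emergency visits are near zero at week 0.* The wording of 4.2.6 screens out only some of them.
- *The pandemic turned reduced care into apparent savings.* Clarification Memo #3 tells sites to contact participants to "inform them of the temporary pause in all study visits". It says nothing about healthcare outside the study, and the documents give no enrolment dates. A visit held on the day a pause began would in any case recall the 28 days before it.
- *The per-person figure can be multiplied by 400.* Component 4 accrues to people who attain SVR, so the enrolled total is not the multiplier.

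**Conclusion.** The point holds for hospital nights and for the week 72 versus week 48 contrast, and on both counts section 12.3 is wrong as written. The first rests on the documents alone: a 28-day recall lies inside a 35-day exclusion, with no matching screen later. The second follows by algebra for any saving that is stable between weeks 48 and 72. A saving still growing or fading over that interval would show only its drift. It also relies on both visits following SVR, which is the normal schedule (section 3.0), though a late SVR visit is allowed up to week 72.

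The size, 0.24 to 2.4 spurious nights per SVR responder, is an illustration. It assumes a background of 0.02 to 0.2 nights per 4 weeks, no hospital nights at week 0 and no effect of cure. It has not been turned into currency, so its weight against drug and visit costs is unknown. The net direction over all three items cannot be determined from the documents.

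The scope is component 4 of the healthcare-sector perspective, under exploratory objective 1.4.5. The program perspective and the primary SVR and SAE analyses are unaffected.

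**What to change.** In Protocol 12.3 (component 4 and its sensitivity analyses) and 12.6.2, or in the separate analysis plan that will cover this objective:

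- Delete the week 72 versus week 48 contrast as an estimate of SVR savings. Replace it with a zero-saving scenario that uses components 1 to 3 only.
- Report component 4 separately for hospital nights, emergency visits and office visits. Add a sensitivity analysis that sets the hospital-night change to zero or varies it over a stated range.
- Replace the wording that attributes the difference to SVR with *observed change*. Name the eligibility effect on week 0 hospital use beside the biases that section 12.3 already lists.

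No new data are needed, since 6.3.15 already collects the three items separately. The cost is a few extra lines of analysis and a weaker causal statement, and the design cannot support the stronger one.
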